4.2.1.2 CHRONIgAN study

1. Males and females aged 18 to 75 years.
2. Written informed consent form.
3. Biopsy-proven idiopathic IgAN with chronic (T1,2) or moderate (M0,1, S0,1, E0, T0, C0) renal lesions at high or very high CKD risk within 4 weeks.
4. eGFR ≥ 30 ml/min/1.73 m².
5. 24-hour proteinuria ≥ 0.5 g.
6. Patients on treatment or candidate for the treatment with RASBs (either an ACEi or ARB), as per clinical practice, according to the current KDIGO guidelines.

4.2.2 Exclusion criteria

1. Non biopsy-proven IgAN
2. IgAN patients with minimal change disease at kidney biopsy and nephrotic syndrome.
3. IgAN patients with macrohematuria and acute renal failure.
4. IgAN patients with rapidly progressive glomerulonephritis (extracapillary lesions in more than 25 % of glomeruli in the kidney biopsy).
5. Patients with secondary IgAN (lupus nephritis, Schoenlein-Henoch purpura, liver cirrhosis).
6. Patients with superimposed IgAN in a kidney transplant.
7. Patients with other types of glomerular diseases
8. Patients with solitary kidney
9. Patients with end-stage kidney disease
10. Bleeding disorders not responsive to treatment
11. Patients with myocardial infarction or cerebrovascular stroke in the previous six months.
12. Severe liver diseases, infections, malignancies.
13. Uncontrolled diabetes (glycemia > 200 mg/dL and HbA1c $> 7.5\%$).

14. Aseptic necrosis of any bone.
15. Any prior immunosuppressive therapy.
16. Other morbidities that can be exacerbated by corticosteroids.
17. Previous adverse side effects and/or contraindications to RASBs and SGLT2is.
18. Pregnancy and breastfeeding.
19. If women of childbearing potential (WOCBP): patients not available to use highly effective contraceptive measures during the study treatment period and up to one month after the last dose of study drugs.

4.3 Interventions

4.3.1 Study treatments (dosage and rationale)

Study drugs (already been placed on the market as authorized medicinal products) will be not supplied by the study Sponsor and will be administered according their labelling and no additional labelling will be required to ensure subject safety and the reliability and robustness of data generated in this clinical trial.

For all information about study drugs, please refer to their respective Summary of Product Characteristics (SmPCs).

RASBs

Patients will receive treatment with renin-angiotensin system blockers, RASBs (either angiotensin-converting enzyme inhibitor, ACEi, or angiotensin II receptor blocker, ARB) as per clinical practice, according to the current KDIGO guidelines.

For example, Ramipril will be administered at dosage of 5 mg x 2 times per day (8.00-20.00) in patients with blood hypertension. Then, it will be increased of 2.5 mg x 2 per day every three days until the reduction of hypertension and proteinuria.

In patients with normal arterial blood pressure Ramipril will be administered at dosage of 2.5 mg x 2 times a day

In patients no tolerant to Ramipril, a sartan will be administered, i.e. Losartan 12.5 mg x 2 times a day. A gradual increase of 6.25 mg (two times a day) will be done to reduce proteinuria.

Rationale: RASBs will be administered to reduce blood pressure at glomerular level and proteinuria (39,40).

Dapagliflozin

The drug will be administered at dosage of 10 mg per day as reported in other randomized clinical trials in which Dapagliflozin has been administered in combination with RASBs (29,31).

Rationale: To reduce blood pressure at glomerular level and proteinuria.

Corticosteroids

AClIgAN trial

Methylprednisolone will be administered at dosage of 15 mg/kg body weight until the dosage of 1 gr in the first day and 50% reduced dose in the other two days and then Prednisolone at dosage of 0.5 mg/kg body weight at alternate days will be administered until the end of the month. This treatment will be repeated for 3 consecutive months. After 3 months, prednisone will be gradually reduced of 25% of the dosage every week until the end of treatment (4 weeks).

Rationale: To care the active renal lesions represented by endocapillary and extracapillary glomerular lesions. This treatment has been used in other clinical trials of IgAN (12,18,43).

CHRONlIgAN trial

Patients will receive oral corticosteroids therapy for six months (prednisone 0.4 mg/kg body weight for 2 months and then gradual reduction of 5 mg/day for 4 months) combined with RASBs and, then, RASBs alone for a total of 36 consecutive months.

Rationale: To care the moderate and chronic renal lesions in non-responders to RASBs alone as suggested by the KDIGO guidelines (4,5).

4.3.2 Lifestyle modifications and other therapy

Concomitant therapy

Eradication of infectious foci, or concurrent antibiotic therapy to prevent infections or to avoid the transformation of a trivial infection into a severe complication will be considered. In presence of reduced kidney function ($eGFR < 30 \text{ ml/min/1.73 m}^2$) patients will receive reduced doses of nephrotoxic antibiotics.

Non-steroidal anti-inflammatory drugs and other nephrotoxic drugs will be avoided.

Due to the short term of corticosteroid therapy, IgAN patients will not receive supplementary therapy for osteoporosis. However, the physician will decide, in every patient, the supplementary therapy.

Inactivated pneumococcal and influence vaccines will be administered. Cotrimoxazole will be administered as *Pneumocystis jirovecii* prophylaxis.

COVID-19 Vaccine will be administered also in IgAN patients who will be enrolled in the arm of corticosteroids.

Patients treated with corticosteroids will receive ciprofloxacin before and during the two weeks following the meningococcal vaccination.

In presence of hypertension, anti-hypertensive drugs will be mainly replaced by RASBs to reduce hypertension and proteinuria.

Diuretics will be administered. Thiazides will be replaced by loop diuretics in presence of impairment of the renal function less than $30 \text{ ml/min/1.73 m}^2$.

Cardioprotective drugs will be administered in presence of cardiac insufficiency.

Statins will be prescribed in presence of hypercholesterolemia (> 200 mg/dL). Allopurinol will be administered in presence of hyperuricemia. It will be reduced if patients will have an impairment of the renal function less than 30 ml/min/1.73 m².

Cimetidine will not be prescribed because it interferes with serum creatinine measurements. Other gastroprotective drugs will be administered.

In presence of persistent or permanent eGFR <15 ml/min/1.73 m² patients will receive periodic hemodialysis or peritoneal dialysis.

Any other immunosuppressive therapies e.g. mycophenolate mofetil, cyclophosphamide or azathioprine will be not permitted in this study, unless there will be other definite indications for using these drugs.

Rifampin will be also prohibited from this study as it interacts with methylprednisolone and makes the study drug less effective.

Life style modifications

4.3.3 Women of childbearing potential

A woman is considered of childbearing potential (WOCBP), i.e. fertile, following menarche and until becoming post-menopausal unless permanently sterile. Permanent sterilisation methods include hysterectomy, bilateral salpingectomy and bilateral oophorectomy. A postmenopausal state is defined as no menses for 12 months without an alternative medical cause.

For WOCBP, a negative highly sensitive urine or serum pregnancy test will be done to include the patient in the trial.

Additional pregnancy testing during the trial will be performed if clinically indicated.

In each case of delayed menstrual period (over one month between menstruations) confirmation of absence of pregnancy will be ascertained. This protocol will be also applied to WOCBP with infrequent or irregular menstrual cycles.

The inclusion of WOCBP will require use of highly effective contraceptive measures during the study treatment period and up to one month after the last dose of study drugs.

According to the current version of “Recommendations related to contraception and pregnancy testing in clinical trials” of the *Clinical Trials Facilitation and Coordination Group*, methods that can achieve a failure rate of less than 1% per year when used consistently and correctly will be considered as highly effective birth control methods. Such methods will include:

- combined (estrogen and progestogen containing) hormonal contraception associated with inhibition of ovulation:
 - oral
 - intravaginal
 - transdermal
- progestogen-only hormonal contraception associated with inhibition of ovulation:
 - oral
 - injectable
 - implantable
- intrauterine device (IUD)
- intrauterine hormone-releasing system (IUS)
- bilateral tubal occlusion
- vasectomized partner
- sexual abstinence.

4.4 Outcome measures

The primary endpoint is the 24 h-proteinuria reduction between arms as suggested by Inker LA et al (44). It will be assessed after 4 and 8 months in the ACiGaN study and after 10 months in the CHRONiGaN trial.

The secondary end point is the GFR slope calculated as the mean of individual slope obtained from individual linear regression of eGFR overtime (3 years). Based on the International Consensus definition of clinical trial outcomes for kidney failure (23) we have also considered other secondary end points listed below.

Primary and secondary end points that will be evaluated in the two RCTs are listed below:

Primary endpoint:

- Between-arms difference in proteinuria reduction within 4 and 8 months in ACiGaN and within 10 months in CHRONiGaN study.

Secondary endpoints:

- eGFR slope calculated as mean of individual slope obtained from individual linear regression of eGFR overtime (3 years);
- eGFR decline > 40 % from the baseline value;
- composite end point: GFR decline > 40%, ESKD (defined as long-term GFR \leq 15 ml/min/1.73m² for more than three months or need for maintenance dialysis or kidney transplantation) or death due to kidney disease;
- absolute difference between last GFR value and baseline GFR;
- stable renal function defined as a decline in GFR \leq 5 ml/min/1.73m² at the end of three years follow-up;
- mean annual change in the slope of the reciprocal of serum creatinine concentration;
- time-averaged proteinuria (TA-P) calculated as the weighted mean of all post-randomization measurement, with weights representing the time elapsed since the previous measurement;
- proteinuria slope, calculated as a mean of individual slope, obtained from individual linear regression of daily proteinuria overtime (3 years);
- complete remission of proteinuria defined as achievement of urinary protein level \leq 0.2 g/day or a urinary protein-to-creatinine ratio \leq 0.2 g/g;
- partial remission of proteinuria defined as achievement of a urinary protein reduction \geq 50% or greater compared with baseline value.

The end points will be evaluated monthly in IgAN patients with active renal lesions in the first eight months after kidney biopsy and then every three months. In IgAN patients with chronic or moderate renal lesions the end points will be evaluated every three months in the first two years after the enrollment and then every six months.

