
Endpoints
	
Primary endpoint:
 
 • Between-arms difference in proteinuria reduction within 4 months and in non-responders within 8 months in ACiGaN study. • Between-arms difference in proteinuria reduction within 10 months in CHRONiGaN study. 
Secondary endpoints:
 
 • eGFR slope calculated as mean of individual slope obtained from individual linear regression of eGFR overtime (3 years); • eGFR decline > 40 % from the baseline value; • composite end point: GFR decline > 40%, ESKD (defined as long-term GFR ≤ 15 ml/min/1.73m² for more than three months or need for maintenance dialysis or kidney transplantation) or death due to kidney disease; • absolute difference between last GFR value and baseline GFR; • stable renal function defined as a decline in GFR ≤ 5 ml/min/1.73m² at the end of three years follow- up; • mean annual change in the slope of the reciprocal of serum creatinine concentration;

	
 time-averaged proteinuria (TA-P) calculated as the weighted mean of all post-randomisation measurement, with weights representing the time elapsed since the previous measurement; proteinuria slope, calculated as a mean of individual slope, obtained from individual linear regression of daily proteinuria overtime (3 years); complete remission of proteinuria defined as achievement of urinary protein level ≤ 0.2 g/day or a urinary protein-to-creatinine ratio ≤ 0.2 g/g; partial remission of proteinuria defined as achievement of a urinary protein reduction $\geq 50\%$ or greater compared with the baseline value.
Number of Sites	Over 30
Number of patients	
432 patients:
 
 132 patients (66 patients per group, including a 10% dropout rate, in the ACiGaN trial) 300 patients (150 patients per group, including a 10% dropout rate, in the CHRONiGaN trial)

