1.2. Rationale

In our CLlIgAN study, we have planned to evaluate:

- (i) The effect of early start corticosteroid therapy combined with RASBs (experimental arm) versus RASBs alone in IgAN patients with active renal lesions (AClIgAN) who will receive corticosteroids after 4 months of RASBs (standard care) in presence of persistent proteinuria ≥ 0.5 g/24 hours and eGFR ≥ 30 ml/min/1.73 m² (control arm).
- (ii) The effect of SGLT2i (dapagliflozin) combined with RASBs (experimental arm) versus corticosteroids combined with RASBs (control arm) in IgAN patients with chronic or moderate renal lesions (CHRONlIgAN) after a run-in phase of 4 months in which they will receive RASB therapy alone (standard care).

In both studies patients enrolled in the control arms will be treated according to the evidence-based recommendations (standard care) provided within the KDIGO guidelines.

In conclusion, we would like to evaluate the effect of early start corticosteroids in IgAN patients with active renal lesions (AClIgAN) and to spare corticosteroids therapy in IgAN with chronic or moderate renal lesions (CHRONlIgAN) administering Dapagliflozin.

We would also provide earlier ESKD risk prediction by using our tool DialCheck (32).

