2.1 Primary objectives

- To evaluate the therapeutic effect on proteinuria with early corticosteroid therapy, administered after the kidney biopsy in IgAN patients with active renal lesions (AClGaN) versus standard care of RASBs alone followed by corticosteroids combined with RASBs;
- To evaluate the therapeutic effect of SGLT2i (Dapagliflozin) combined with RASBs on proteinuria versus corticosteroids combined with RASBs in patients with chronic or moderate renal lesions (CHRONlGaN); thus, to avoid the potential side effects of corticosteroid therapy.

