3. TRIAL DESIGN

This project encompasses two prospective, multicentre, open-label randomized controlled clinical trials (RCTs) of IgAN patients (CLlGaN) based on the kidney biopsy report (*Figure 1*).

Stratified randomization will be done by age and sex in renal centers.

[figure not shown]

Figure 1

ACiGaN TRIAL

Patients with active renal lesions (E1 and/or C1) in the presence of $GFR \geq 30$ ml/min/1.73 m² and proteinuria ≥ 0.5 g/24 hours will be randomized into two arms:

- 1) corticosteroids combined with RASBs for 4 months followed by RASBs alone (experimental arm);
- 2) RASBs alone for 4 months followed by the combination corticosteroids and RASBs for 4 additional months and then only RASBs (standard care) as suggested by KDIGO guidelines (5).

Participants assigned to the experimental arm will receive by 2 weeks from the kidney biopsy (pulse) methylprednisolone (SOLU-Medrol) 500-1000 mg in the first day and then 50% of dose in the next two days followed by oral prednisone (0.5 mg/kg/bw) on alternate days until the end of the month. This treatment will be repeated for three consecutive months. After three months, participants will gradually reduce oral prednisone, in the course of four weeks. Next, they will receive RASBs alone.

The daily dose of methylprednisolone will be individualized (15 mg/kg), based on the ideal body weight. The drug will be administered in a single dose intravenously for 30-60 min. To avoid obesity and diabetes corticosteroids will be administered only in the morning.

This is a parallel group, two arm, superiority trial with 1:1 allocation ratio.

As per standard care RASB therapy will be titrated to its maximum labelled or tolerated dose as anti-proteinuric effect in every patient.

Rationale of the study design

Corticosteroids at high dosage have been administered in RCTs of IgAN (18,41) independent of the type of renal lesions despite empiric evidence from clinical practice and strong and consistent evidence from observational studies that the lesions identified at kidney biopsy may play a role in the response to treatment. Our aim is to evaluate the benefit of early pulse therapy combined with oral prednisone only in IgAN patients with active renal lesions. In our protocol, we have excluded intensive immunosuppressive therapy (CS+CYP/AZA/MMF) because RCTs have demonstrated that the potential benefits-harms trade off is in favour of the harms (42).

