6. SAMPLE SIZE AND STATISTICAL METHODS

ACIGAN. Data from the literature (22,23) have shown a difference in renal survival between corticosteroids and controls when the researchers assumed a difference of 50% in the primary end point (i.e. in the between-arms difference of delta 24 hour proteinuria from baseline to 6 months) as clinically relevant. Therefore, we assume that a mean delta proteinuria from baseline to 6 months in patients treated with RASBs alone (control arm) is 0.6 ± 1.0 g/24 hours (\pm SD) versus a mean delta proteinuria that is 1.2 ± 1.0 g/24 hours (\pm SD) from baseline to 6 months in patients treated with RASBs and corticosteroids (experimental arm). Based on these assumptions, we calculated a sample size of

132 patients (66 patients per group including a 10% dropout rate) for a power of 90%, a two-sided significance level of 0.05 and 3 years of recruitment. If the number of the enrolled patients will be insufficient, the recruitment period will be extended for two years.

CHRONiGaN. Data from the literature (29-31) have shown a difference of renal survival between SGLT2is and controls. There are no data in the literature exploring the difference of renal survival or proteinuria between SGLT2is and steroids. Here, the researchers assumed an opportunistic sample of 300 patients for this first comparative study (150 patients per group, including a 10% dropout rate).

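### At month 4 the ACiGaN control arm has had RASBs only, so the month-4 primary comparison cannot by itself show that early corticosteroids beat RASBs followed by corticosteroids

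*Protocol*

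**What the plan says.** **Objective.** Protocol Section 2.1 compares early corticosteroids "versus standard care of RASBs alone followed by corticosteroids combined with RASBs". The comparator is a sequence. The design rationale in Section 3 takes the same view: the worry is that active lesions become chronic while steroids are withheld.

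**Treatment schedule.** Section 3 gives the experimental arm as "corticosteroids combined with RASBs for 4 months followed by RASBs alone (experimental arm") and the control arm as "RASBs alone for 4 months followed by the combination corticosteroids and RASBs for 4 additional months and then only RASBs (standard care"). Section 1.2 describes the controls as patients "who will receive corticosteroids after 4 months of RASBs (standard care) in presence of persistent proteinuria" and an adequate eGFR, so there the control course is conditional.

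**Endpoint.** Section 4.4 names months 4 and 8 together: "Between-arms difference in proteinuria reduction within 4 and 8 months in ACiGaN and within 10 months in CHRONiGaN study". The synopsis has a different wording: "Between-arms difference in proteinuria reduction within 4 months and in non-responders within 8 months in ACiGaN study".

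**Sample size.** Section 6 assumes that the mean fall from baseline to 6 months "in patients treated with RASBs alone (control arm) is 0.6 ± 1.0 g/24 hours", against 1.2 ± 1.0 with RASBs plus corticosteroids. It sets 90% power, two-sided alpha 0.05, and 66 patients per arm including 10% dropout. Section 6.4 also describes the primary comparison at 6 months.

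**The concern.** A primary time point should measure the contrast that the objective names. At month 4 the experimental arm has finished its steroid course and the control arm has not begun one. A month-4 difference shows that steroids plus RASBs lower proteinuria more than RASBs alone. It cannot show whether waiting four months loses any of that benefit, because nobody in the control arm has yet been treated after the wait.

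The other passages add to the difficulty. On the synopsis wording, month 8 is confined to non-responders, which leaves month 4 as the only primary comparison in all randomised patients. Section 7.3 plans an interim look at the primary endpoint once half the patients have 6 months of follow-up, with possible interruption for benefit. A patient who has just reached that mark has a month-4 value and no month-8 value.

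At stake is the sentence the trial can write at the end. A significant month-4 result could be reported as early treatment beating standard care, although the same data would be expected if delayed steroids catch up completely.

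**Working it through.** **1. What each arm has received (Sections 1.2 and 3)**

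| Month | Experimental arm | Control arm | Contrast |
|---|---|---|---|
| 4 | course just finished | RASBs only | steroids + RASBs vs RASBs alone |
| 6 | 2 months after course | midway through course, if given | mixed |
| 8 | 4 months after course | course just finished, if given | early vs delayed, unequal time since steroids |
| 12 | 8 months after course | 4 months after course, if given | early vs delayed, both arms well past the course |

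Only from month 8 can both arms have completed what they were assigned.

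**2. The plan's own figure.** Inputs from Section 6: difference 1.2 − 0.6 = 0.6 g/24 h, SD 1.0, power 90%, two-sided alpha 0.05.

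n per arm = 2 × (1.960 + 1.282)² × 1.0² / 0.6² = 58.4, so 59. With 10% dropout: 59 / 0.9 = 65.6, so 66 per arm and 132 in total. This matches. The t-test version needs 59.4, so 60 per arm.

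**3. The month-4 test.** Assumption: the 0.6 g difference, stated for 6 months, applies at month 4. With 59 evaluable per arm, the standard error is √(2/59) = 0.184 and 0.6 / 0.184 = 3.26. Power is Φ(3.26 − 1.96) = 0.903 (normal approximation), or 0.898 from the noncentral t. With 60 per arm the t value is 0.903; with all 66 it is 0.928.

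**4. If the month-4 effect differs (t-test, SD 1.0)**

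| True month-4 difference | n = 59 | n = 60 | n = 66 |
|---|---|---|---|
| 0.6 g | 0.898 | 0.903 | 0.928 |
| 0.5 g | 0.768 | 0.775 | 0.814 |
| 0.4 g | 0.577 | 0.584 | 0.626 |
| 0.3 g | 0.366 | 0.371 | 0.402 |

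None of these depends on the month-8 difference. If that is truly zero, a month-8 test rejects 5% of the time.

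**5. From month 4 to the whole trial.** Take a month-4 difference of 0.6 g, a month-8 difference of 0 and 59 per arm. If the two tests were uncorrelated:

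- either suffices: 1 − (1 − 0.903) × 0.95 = 0.908
- both required: 0.903 × 0.05 = 0.045

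Simulation with correlation from 0 to 0.9 (an assumed range) gives 0.908 to 0.927 for either, and 0.045 down to 0.026 for both.

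**6. What month 8 can detect.** If SD 1.0 also holds at month 8, 59 per arm detect (1.960 + 1.282) × 0.184 = 0.60 g with 90% power and (1.960 + 0.842) × 0.184 = 0.52 g with 80% power. On the planning means, 0.6 g is what remains at month 8 if delayed steroids add nothing and the early gain is fully kept. Any catch-up leaves less.

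**The case against.** The month-4 contrast is open and deliberate. Section 1.2 itself sets early corticosteroids with RASBs against RASBs alone, and Section 6 sizes the trial on that contrast. At month 4, RASBs alone is what standard care prescribes, so the comparison is a valid randomised one of two strategies at that time. An earlier fall in proteinuria is a real effect. All of this stands. It supports keeping the month-4 comparison, but not letting it answer a question about delayed steroids.

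A reader might infer that the trial would be positive 90% of the time even if early start had no advantage, so that its question is answered yes by design. The documents do not support that:

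- The 90% is planned power under a real month-4 difference, not a false-positive rate. If the arms do not differ at month 4, that test rejects 5% of the time.
- *No advantage* here can only mean none remaining at month 8.
- The protocol does not say that month 4 alone makes the trial positive. If both time points are required, the figure is at most 5%.

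It is also not settled that month 4 is the analysed time point. Section 6.4 uses 6 months, and the primary-endpoint row of Figure 2A appears to start at month 6, although the table may have been misread.

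Month 8 is not a clean reference either, because controls have only just stopped steroids while the experimental arm stopped four months earlier. Later proteinuria and eGFR outcomes are planned as secondary endpoints, so catch-up would be visible. That limits the harm but does not say which result carries the conclusion.

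**Conclusion.** The point holds as one of interpretation. The month-4 part of the ACiGaN primary endpoint compares corticosteroids + RASBs with RASBs alone and cannot alone establish early corticosteroids over RASBs followed by corticosteroids. This follows from the treatment schedule and needs no numerical assumption.

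Its size does rest on assumptions. With 59 to 60 evaluable per arm, the month-4 test is significant about 90% of the time if the 6-month planning difference applies at month 4, and 37 to 78% of the time for differences of 0.3 to 0.5 g, whatever happens by month 8. This carries over to the trial as a whole only if success at month 4 is enough, which the protocol leaves open (91–93% against at most 5%). No choice of alpha or sample size would make month 4 informative about delayed treatment, so the issue is separate from multiplicity.

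**What to change.** Amend the synopsis and Sections 4.4, 6 and 6.4 before any unblinded look at the primary endpoint:

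1. Label the month-4 comparison *corticosteroids + RASBs versus RASBs alone*, and state that it does not alone establish early treatment over standard care.
2. Base the early-versus-standard-care conclusion on the month-8 between-arm difference in all randomised patients, replacing the synopsis restriction to non-responders. This agrees with the intention-to-treat rule in Sections 6.4 and 6.5.
3. Report the existing month-12 visit as a check, because controls have just finished steroids at month 8.
4. Reconcile the 4-, 6- and 8-month time points. Also reconcile Sections 1.2 and 3 on whether the control course is conditional on persistent proteinuria, since this determines what the month-8 control arm represents.
5. State that the 90% power refers to corticosteroids versus RASBs alone, and give a detectable difference for month 8 with its assumed SD.

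No added visit or measurement is needed. The downside is that 90% power can no longer be claimed for the primary conclusion, and the month-8 comparison may be underpowered if delayed steroids recover part of the gap.
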